2 INTRODUCTION

2.1 Indication

MYL-1501D is being developed as a follow-on biologic (US terminology) or biosimilar (EU terminology) to Lantus®.

2.2 Background and Rationale

Insulin secretion in healthy subjects is characterized by relatively constant basal insulin secretion with a post-prandial surge. Type 1 diabetes mellitus (T1DM) is characterized by loss of the insulin-producing beta-cells of the islets of Langerhans in the pancreas, leading to a deficiency of insulin. The main cause of beta-cell loss is a T-cell mediated autoimmune attack [1]. The principal treatment of patients with T1DM is initiation of insulin and diet control and careful monitoring of blood glucose levels.

The Diabetes Control and Complications Trial [2] and other trials [3] provide conclusive evidence that maintaining tight glycemic control can prevent or delay microvascular and macrovascular complications in patients with T1DM. A number of different insulin regimens have been proposed for treatment of patients with T1DM. It is generally accepted that the so-called basal-bolus insulin regimen (1 or 2 daily injections of long/intermediate-acting insulin covering basal insulin requirements in combination with 3 daily injections of short-/rapid acting insulin to cover meal-related insulin requirements) generally yields the best glycemic control in diabetes. Clear targets for plasma glucose levels have been recommended for basal-bolus insulin regimens [4].

Different insulin preparations are available for management of basal insulin requirements, including intermediate-acting insulins (neutral protamine Hagedorn insulin) and long-acting insulin analogs such as insulin glargine and insulin detemir. Long-acting insulin analogs have proven efficacy and offer good glucose control over 24 hours for a single dose. Insulin glargine is a long-acting insulin analogue allowing once-daily administration to cover basal insulin requirements for over 24 hours. After injection of Insulin glargine into the subcutaneous tissue, the acidic solution is neutralized; leading to formation of micro-precipitates from which small amounts of insulin glargine are continuously released, providing a smooth, peakless, predictable concentration versus time profile with a prolonged duration of action.

MYL-1501D is a human insulin analogue of r-DNA origin produced in the host organism *Pichia pastoris*. *P. pastoris* is a methylotropic yeast that has been successfully used in the production of proteins.

The aim of this study is to demonstrate similar efficacy and safety between MYL-1501D product produced from two manufacturing processes in combination with insulin lispro in patients with T1DM.

Since the two investigational products have an identical presentation of prefilled pen to be used by the subjects during the treatment period, the subject and the treating physician will remain blinded to treatment assignment. Furthermore, the evaluation of the study endpoints, such as analysis of immunogenicity and glycosylated hemoglobin (HbA1c), will be performed in a blinded manner by blinded personnel. The sponsor team as well as the CRO team will also be blinded to the subject assigned treatment.

To ensure that both treatment arms are comparable at baseline with respect to drug-induced immune responses and other parameters, only subjects who have been on a stable dose of Lantus® for at least 3 months prior to screening will be included.

During the 4-week run-in period with Lantus® and Humalog®, the dose of insulin will be titrated (if required) to ensure diabetes control. The run-in period ensures comparable drug exposure for all subjects, and increases the likelihood of comparable immune responses at the start of the treatment period. An 18-week treatment period is an adequate period to detect differences in HbA1c of the treatment arms [5].

Dosing with MYL-1501D during treatment period and Lantus® during run-in period will be guided by self-monitored blood glucose (SMBG)-based glucose level assessments and by the titration committee as detailed in the insulin monitoring (titration committee) plan.

Rescue criteria based on HbA1c are defined based on week 12 HbA1c measurement, so that a potential worsening of metabolic control in subjects during the study can be identified and therapy modified at the discretion of the investigator.

A follow-up visit, 2 weeks after the end of treatment, will ensure the safety of all subjects after they stop the study medication and return to receiving approved medications.

Complete information for the study medication can be found in MYL-1501D Investigator's Brochure (IB). [6]

2.2.1 Rationale for Dose Selection

Only subjects who have been on a stable dose of Lantus® for at least 3 months prior to screening will be included in the study, thus subjects would be on a stable dose at study entry. If required, subject dose should be adjusted during the 4-week run-in period to stabilize the subjects. During the treatment period, dose adjustment should be avoided but it is permitted to ensure subject's stable state and safety.

3 OBJECTIVES AND ENDPOINTS

3.1 Objectives

3.1.1 Primary objectives

To test whether MYL-1501D product from Process VI once daily is non-inferior to MYL-1501D product from Process V once daily based on change in HbA1c from baseline to week 18 when administered in combination with mealtime insulin lispro.

3.1.2 Other objectives

To compare MYL-1501D product from Process VI and Process V at week 18, when administered in combination with mealtime insulin lispro, with respect to:

- Immunogenicity: incidence and change from baseline in the relative levels of anti-drug antibody
- Hypoglycemic events: incidence and rate per 30 days
- Occurrence of local reactions, systemic reactions and other adverse events
- Device-related safety assessment
- Change in fasting plasma glucose from baseline
- Change in insulin dose per unit body weight (U/kg) from baseline
- Change in 8-point SMBG profile from baseline

3.2 Endpoints

3.2.1 Primary Endpoints

The primary efficacy endpoint is change in HbA1c from baseline to week 18 for the ITT population.

3.2.2 Secondary Endpoints

3.2.2.1 Efficacy

- Change in fasting plasma glucose from baseline
- Change in basal insulin, meal-time, and total insulin dose per unit body weight (U/kg) from baseline
- Change in 8-point SMBG profile from baseline

3.2.2.1 Safety

- Incidence of positive antibody response and change in antibody percentage binding from baseline.
- Change in hypoglycemia rate (30 day adjusted) from baseline and incidence of hypoglycemic events
- Incidence of treatment-emergent adverse events (TEAEs) and serious adverse events (SAEs)
- Incidence of local reactions, systemic reactions and other adverse events
- Incidence of device-related safety assessment

4 STUDY POPULATION

4.1 Study Population

A total of 202 subjects with T1DM are planned to be randomized in this study, to receive MYL-1501D from either Process VI or Process V with a randomization ratio of 1:1.

A detailed description related to sample size determination is provided in [Section 7](#).

4.2 Inclusion and Exclusion Criteria

4.2.1 Inclusion Criteria

Subject eligibility should be reviewed and documented by an appropriately qualified member of the investigator's study team before subjects are included in the study.

Subjects must meet all of the following inclusion criteria to be eligible for enrolment into the study:

1. Written and signed informed consent needs to be provided by subjects or their legal representatives before starting any protocol-specific procedures.
2. Male and female subjects between the ages of 18 to 65 years, both ages inclusive.
3. Subjects with an established diagnosis of T1DM per American Diabetes Association (ADA) 2017 criteria who also fulfil the following criteria:
 - a. Initiation of insulin treatment within 6 months of T1DM diagnosis
 - b. Treatment with basal-bolus insulin therapy for at least 1 year before screening
 - c. Fasting plasma C-peptide <0.3 nmol/L (0.9 ng/mL) at screening
 - d. Subject has been on once daily Lantus® or once daily Levemir® or once daily Toujeo® at stable dose ($\pm 15\%$ variation in dose) for at least 3 months at screening
4. Body mass index (BMI) of 18.5 to 35 kg/m² at screening (both values inclusive).
5. Stable weight, with no more than 5 kg gain or loss in the 3 months prior to screening, this information will be collected by subject interview during medical history.
6. HbA1c $\leq 9.5\%$ at screening.
7. Hemoglobin ≥ 9.0 g/dL at screening.
8. Subject has the capability of communicating appropriately with the investigator.
9. Subject is able and willing to comply with the requirements of the study protocol including the 8-point SMBG, completion of subject diary records and following a recommended diet and exercise plan for the entire duration of the study.
10. Female subjects of childbearing potential who are willing to use oral contraception or acceptable methods of contraception, (e.g., intra-uterine device, spermicidal gel plus

condom, diaphragm plus condom, etc.), from the time of screening and for the duration of the study, through study completion.

- a. Periodic abstinence (e.g., calendar, ovulation, symptothermal, post-ovulation methods) and withdrawal are not acceptable methods of contraception.
- b. Postmenopausal females must have had no regular menstrual bleeding for at least 1 year prior to screening.
- c. Female subjects who report surgical sterilization must have had the procedure at least 6 months prior to screening.
- d. All female subjects of childbearing potential must have negative pregnancy test results at screening and at clinic visits, as per the SCHEDULE OF ACTIVITIES (SOA).
- e. If female subjects have male partners who have undergone vasectomy, the vasectomy must have occurred more than 6 months prior to screening

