	
diagnosis
 
b. Treatment with basal-bolus insulin therapy for at least 1 year before screeningc. Fasting plasma C-peptide <0.3 nmol/L (0.9 ng/mL) at screeningd. Subject has been on once daily Lantus® or once daily Levemir® or once daily Toujeo® at stable dose ($\pm 15\%$ variation in dose) for at least 3 months at screening 
4. Body mass index (BMI) of 18.5 to 35 kg/m² at screening (both values inclusive).5. Stable weight, with no more than 5 kg gain or loss in the 3 months prior to screening, this information will be collected by subject interview during medical history.6. Glycosylated hemoglobin (HbA1c) $\leq 9.5\%$ at screening.7. Hemoglobin ≥ 9.0 g/dL at screening.8. Subject has the capability of communicating appropriately with the investigator.9. Subject is able and willing to comply with the requirements of the study protocol including the 8-point self-monitored blood glucose (SMBG), completion of subject diary records and following a recommended diet and exercise plan for the entire duration of the study.10. Female subjects of childbearing potential who are willing to use oral contraception or acceptable methods of contraception, (e.g., intra-uterine device, spermicidal gel plus condom, diaphragm plus condom, etc.), from the time of screening and for the duration of the study, through study completion.
a. Periodic abstinence (e.g., calendar, ovulation, symptothermal, post-ovulation methods) and withdrawal are not acceptable methods of contraception.b. Postmenopausal females must have had no regular menstrual bleeding for at least 1 year prior to screening.c. Female subjects who report surgical sterilization must have had the procedure at least 6 months prior to screening.d. All female subjects of childbearing potential must have negative pregnancy test results at screening and at clinic visits, as per the SCHEDULE OF ACTIVITIES (SOA).e. If female subjects have male partners who have undergone vasectomy, the vasectomy must have occurred more than 6 months prior to screening 
Exclusion Criteria
 
1. History or presence of a medical condition or disease that in the investigator's opinion would place the subject at an unacceptable risk from study participation.2. History of hypersensitivity to any of the active or inactive ingredients of the insulin/insulin analogue preparations used in the study, OR history of significant allergic drug reactions.3. History of use of animal insulin within the last 3 years or use of approved biosimilar insulin glargine at any time prior to study entry, except for subject who previously participated in MYL-1501D studies and were compliant with the study protocols.

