4.3.2 Females - Childbearing Potential

Female subjects of child-bearing potential must use an acceptable, highly effective method of contraception (i.e. a method with a failure rate <1% when used consistently and correctly) starting from screening through to at least 7 days after the final dose of study drug. For this study, such methods include at least one of the following:

- Abstinence (periodic abstinence is not acceptable).
- Tubal ligation.
- Intrauterine device (IUD) of intrauterine system (IUS).
- Condom with spermicidal foam/gel/film/cream/suppository.
- Male partner who has had a vasectomy for at least 6 months. Male partners with vasectomies of <6 months are NOT considered protected.
- Hormonal contraceptives (oral, injected, transdermal or implanted) with the exception of low dose gestagens, i.e. only containing lynestrenol or norethisterone, since they do not inhibit ovulation and are therefore not considered as highly-effective. The subject must remain on the hormonal contraceptive throughout the study and must have been using hormonal contraceptives for an adequate period prior to the study to ensure effectiveness (e.g., 3 months).

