5.6 Concomitant Medications

All concomitant medications taken during the study (from signing informed consent to post-study follow-up) must be recorded with indication, daily dose, and start and stop dates of administration in the CRF. All subjects will be questioned about concomitant medication at each clinic visit and at follow up.

Medications taken within 28 days prior to screening and prior to dosing with study medication will be documented as a prior medication. Medications taken after dosing with study medication will be documented as concomitant medications.

Other than study drugs, insulin, insulin analogs and other anti-diabetes medications as well as glucocorticoid therapy (oral, intravenous, inhaled or other routes that produce systemic effects) are prohibited during the study (including the run-in period and the treatment period), except in case of rescue medication treatment.

A list of medications that may interfere with the effect of insulin is provided in Table 2. **No drugs listed in this table should be started during the run-in period or treatment period.**

Table 2: Medication not to be started during the Run-in or Treatment period

Drug classes that are known to augment the blood glucose lowering effect of insulin such as:	Drugs and drug classes that are known to decrease the blood glucose lowering effect of insulin such as:

 1. salicylates at doses more than >2 g/day 2. sulfa antibiotics 3. angiotensin converting enzyme inhibitors 4. disopyramide 5. fibrates 6. fluoxetine 7. monoamine oxidase inhibitors 8. propoxyphene 9. pentoxifylline 10. somatostatin analogs 11. bromergocryptine (bromocryptine) 12. anabolic steroids. 	
 1. danazol 2. niacin 3. diuretics 4. sympathomimetic agents 5. glucagon 6. isoniazid 7. somatropin 8. thyroid hormones 9. oral contraceptives 10. estrogens 11. progestogens 12. protease inhibitors 13. phenothiazine derivatives 14. atypical antipsychotic medications (e.g. olanzapine and clozapine).

Subjects will abstain from all prohibited medications as described in the exclusion criteria section of this protocol (Section 4.2.2). Use of prohibited medication during the study will be deemed a protocol deviation and such subjects will be assessed by Mylan or designee regarding the potential need to early terminate study drug (e.g. for safety reasons: see Section 4.3.4).

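### Inclusion criterion 10 accepts diaphragm plus condom and any oral contraceptive; Section 4.3.2 omits the first and sets conditions on the second

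*Protocol*

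**What the plan says.** Criterion 10 in Protocol V2.0 Section 4.2.1 concerns "Female subjects of childbearing potential who are willing to use oral contraception or acceptable methods of contraception". The synopsis has the same criterion, with the examples "intra-uterine device, spermicidal gel plus condom, diaphragm plus condom, etc". In 4.2.1 the examples end, and the duration follows, in the words "condom, diaphragm plus condom, etc.), from the time of screening and for the duration of the study, through study completion". The criterion limits neither the type of oral contraceptive nor the length of prior use, and it does not refer to Section 4.3.2.

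Section 4.3.2 states that women of childbearing potential "must use an acceptable, highly effective method of contraception (i.e. a method with a failure rate <1% when used consistently and correctly", from screening to at least 7 days after the last dose. It then asks for at least one of six kinds of method: abstinence, tubal ligation, an intrauterine device or system, condom with spermicide, a partner vasectomised for at least 6 months, and hormonal contraceptives.

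- The only barrier entry is "Condom with spermicidal foam/gel/film/cream/suppository".
- Hormonal methods are accepted "with the exception of low dose gestagens, i.e. only containing lynestrenol or norethisterone". The stated reason is that these products do not inhibit ovulation and so do not count as highly effective.
- A woman using a hormonal method must stay on it throughout the study, and "must have been using hormonal contraceptives for an adequate period prior to the study to ensure effectiveness (e.g., 3 months").

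Both sides of the comparison are current V2.0 text.

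**The concern.** Section 4.2.1 asks a qualified member of the study team to review and document eligibility before a subject is included, and the numbered criteria are what that person works from. If a criterion names a method as acceptable, the reviewer has no reason to look further. Here it names one method that the operative contraception section does not list, and it accepts a whole class, oral contraception, from which that section removes some products and some users.

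The stake is participant protection. A woman could enter on a method that the protocol's own standard does not recognise. Under Section 4.4 a positive pregnancy test means withdrawal from the study, and under Section 7.1 subjects who discontinue are not replaced. Sites would also lack a clear rule for what counts as a deviation.

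**Working it through.** No arithmetic beyond a count applies, and the plan has no figure to reproduce. The check sets each option named in criterion 10 against Section 4.3.2.

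| Option named in criterion 10 | In the 4.3.2 list? | Condition in 4.3.2 |
|---|---|---|
| Oral contraception | Yes, under hormonal contraceptives | Not a low dose gestagen (lynestrenol or norethisterone only); continued throughout; adequate prior use |
| Intra-uterine device | Yes | None |
| Spermicidal gel plus condom | Yes | None |
| Diaphragm plus condom | No | Not applicable |

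Count: 4 options named; 2 match without condition, 1 matches with conditions, 1 is absent (2 + 1 + 1 = 4). Three of the four therefore appear in 4.3.2.

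Three cases show what the mismatch means in practice:

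1. A woman uses diaphragm plus condom without spermicide. She meets criterion 10 by express example. She has no entry in the 4.3.2 list.
2. A woman takes a norethisterone-only pill. She meets criterion 10, because oral contraception is unqualified. Section 4.3.2 rejects her method by name.
3. A woman is willing to start a combined pill but has no adequate prior use. She meets criterion 10 on willingness. She does not meet the prior-use condition in 4.3.2.

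The second case is the firmest, since it does not depend on whether the 4.3.2 list is complete. The first does: 4.3.2 introduces its list with the word include, and the documents give no failure rate for diaphragm plus condom.

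Safeguard: the pregnancy test row of Table 1 in V2.0 is marked at Visits 1, 6, 8, 10, 12, 13 and 14, which is 7 visits.

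**The case against.** The best defence is that the two sections are layers of one rule. Criterion 10 is a general willingness test with illustrative examples; Section 4.3.2 is the operating requirement. Any method that satisfies 4.3.2 can also satisfy criterion 10. Criterion 9 requires willingness to comply with the protocol, all criteria must be met, and Section 8.4 requires the study to be run as the protocol describes. On that reading, a woman who will not use a 4.3.2 method fails criterion 9, and only a cross-reference is missing.

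Much of this stands. Both sections bind, and stating conditions on oral contraception in a later section is ordinary drafting. What it does not remove is the express approval, inside an eligibility rule, of a method the later section omits, or the absence of any pointer to the conditions. Open-ended wording can add methods, but it cannot reconcile unqualified acceptance of pills with the exclusion of named ones.

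A reader might infer more than the documents support:

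- *That Table 2 contradicts criterion 10.* Section 5.6 says "No drugs listed in this table should be started during the run-in period or treatment period", and the table includes oral contraceptives, estrogens and progestogens. But criterion 10 already requires use from screening, so it never permits a first start in run-in or treatment. There is no conflict.
- *That a pill started at screening can be shown by counting days to fall short of 3 months.* Section 4.3.2 asks for an adequate period, offers 3 months only as an example, and does not define the point at which the study begins.
- *That half of the named options conflict.* Oral contraception is listed in 4.3.2, with conditions. Only one option is absent.

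**Conclusion.** Criterion 10 is wrong as written, and the point is minor. It expressly accepts one method missing from Section 4.3.2 and accepts oral contraception without the conditions that 4.3.2 imposes. A site relying on criterion 10 alone could enrol a woman whose method 4.3.2 does not allow.

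The conclusion assumes that the 4.3.2 list is meant to be complete and that 4.3.2, as the mandatory and more specific text, should govern. The protocol states neither. The norethisterone and lynestrenol exclusion holds without the first assumption.

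The number of women affected is not given, and testing at 7 visits limits the harm. Nothing here bears on type I error, power or the primary estimate. Nor do the documents support inferring that ineligible women were enrolled or that pregnancies resulted. The point does not extend to sub-items 10b or 10c or to Section 4.3.1.

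**What to change.** In Section 4.2.1 and the synopsis, keep the opening of criterion 10 up to the willingness test. Replace the methods that follow with: *a method of contraception listed in Section 4.3.2 (subject to the conditions stated there)*. Keep the existing timing clause, from screening to study completion. This removes diaphragm plus condom, unqualified oral contraception and the open-ended ending.

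The test should remain willingness to use. Requiring that a woman already be using a method would add a restriction found in neither section, because 4.3.2 requires use only from screening. Leave 10b, 10c and 4.3.1 unchanged. In particular, carrying the 4.3.1 postmenopausal definition into 10b would bring in an FSH level that is in neither the schedule of activities nor the laboratory table.

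Adding diaphragm plus condom to 4.3.2 would also align that method, but the sponsor would have to show that it meets the below-1% standard, and the oral contraception mismatch would remain.

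The cost is a wording change in two places at the next amendment and a note to sites, with no new test or visit. A few women using diaphragm plus condom, an excluded gestagen-only pill or a newly started pill would have to use another listed method.
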